## **15.4. Planned Analyses**

Unless otherwise indicated, all testing of statistical significance will be 2-sided, and a difference resulting in a P value of less than or equal to 0.05 will be considered statistically significant. Furthermore, the baseline will be the last assessment before the dosing of study treatment.

Summary statistics will be provided for the variables described in the following sections. For continuous variables, these statistics will typically include the number of subjects, mean, standard deviation (SD), median, minimum, and maximum. For categorical variables, these statistics will typically include the number and percentage of subjects in each category.

## **15.5. Study Subjects and Demographics**

### **15.5.1. Disposition and Withdrawals**

The numbers of subjects randomized, completing, and withdrawing, along with reasons for withdrawal, will be tabulated overall and by treatment group. The number of subjects in each analysis population will be reported.

### **15.5.2. Protocol Deviations**

All protocol deviations will be classified and documented before database lock and will be discussed in the CSR. All protocol deviations, both minors and majors, will be presented in a data listing.

### **15.5.3. Demographics and Other Baseline Characteristics**

Demographic and baseline characteristics (including age, sex, race, weight, and height) will be summarized for each treatment group and for the overall population by descriptive statistics. Medical history and screening clinical laboratory tests will be listed.

Prior and concomitant medications will be summarized by treatment group, by the number and percentage of subjects taking each medication, classified using World Health Organization Drug Dictionary Anatomical Therapeutic Chemical classes and preferred terms.

#### **15.5.4. Exposure**

Since this is a single dose study, study treatment administration will be summarized in terms of total exposure by cohort and treatment group.

#### **15.5.5. General Considerations**

All continuous study assessments will be summarized by treatment and time point (as applicable) using the descriptive statistics n, mean, SD, median, and range (minimum, and maximum).

Categorical assessments will be summarized by treatment and time point (as applicable) using frequency counts and rates of occurrence (%). Changes from baseline for continuous outcomes will be presented as their corresponding continuous measures for post-baseline visits. All study data will be listed by treatment group, subject and time point.

No preliminary rounding will be performed; rounding will only occur after the analysis. Means and medians will be presented with one more decimal place than the precision of the data. Standard deviations will be presented with two more decimal places than the precision of the data. Percentages will be presented with one decimal place. A percentage of 0% or 100% will be reported as 0% or 100%, respectively. Minimums and maximums will be presented with the same precision as the original data.

All analyses will be performed using the SAS System® version 9.3 or higher. The domain (Study data tabulation Model [SDTM]) and analysis (Analysis Data Model [ADaM]) data sets will be taken as input to the SAS programs that generate the report-ready tables, figures and listings. The submission ready SDTM and ADaM data sets will be provided to the sponsor along with display deliveries. The specifications for the domain data sets and analysis data sets will be provided in a separate document.

The following conventions will be used throughout the study analysis:

- Time T0 is the time of completion of study treatment administration.
- Day of surgery is defined as D0
- Assessment visit times are defined by time T0/D0.
- Baseline value is defined as the last valid measurement prior to beginning study treatment administration.
- Change from baseline is defined as post-baseline value minus baseline value.
- Duration of an AE will be computed in days for AEs lasting longer than 24 hours, and as hours for AEs lasting less than 24 hours. Duration in hours will be calculated as the stop date/time of the event minus the start date/time. Duration in days will be calculated by using

stop date minus the start date +1 if AE occur on or after taking study medication. If AE occur prior to the study medication, then the duration will be calculated by using stop date minus the start date. If reported as ongoing at the time of database lock, the duration will be calculated using the date of the last visit or the last date of any AE for the subject in the database, whichever is later. Missing dates will be imputed as described in the Study's Statistical Analysis Plan (SAP).

- The number of days in the study is computed as: [Date of study completion or withdrawal minus the date of study drug administration (Day 1)] + 1.
- If duplicate values are obtained at a given visit (e.g., repeated vital sign measurements), the last value will be used unless it is noted that the measurement was in error for that value. Values that compromise interpretation will not be used in summaries (e.g., values that were obtained post-dose will not be summarized as pre-dose values).

## 15.6. Analysis of Efficacy Measures

All efficacy endpoints (e.g., NRS scores), will be summarized over time by treatment using descriptive statistics including confidence intervals as appropriate.

AUC calculations will be done using the standard trapezoidal rule

$$AUC = \sum_{i=0}^x \left( \frac{NRS_i + NRS_{i+1}}{2} \right) * (T_{i+1} - T_i)$$

Where:  $NRS_i$  = NRS at time  $i$ , and  $(T_{i+1} - T_i)$  is the Time difference in minutes between time  $i$  and time  $i+1$ . A similar calculation and handling of missing data will be performed for the NRS scores with ambulation.

In this study, subjects are permitted to take rescue medication for analgesia. It is expected subjects randomized to placebo arm will take rescue medication more often. During both inpatient and outpatient portions of the study, the subjects will be instructed to record NRS immediately prior (within approximately 15 min) to taking rescue medication.

Missing NRS will be handled as discussed in the Study's SAP and as briefly outlined in [Section 15.6.4](#).

### 15.6.1. Primary Efficacy Analysis

The primary efficacy analysis of the primary endpoint ( $AUC_{0 \text{ to } 96h}$ ) will be conducted using an analysis of variance (ANOVA) model with treatment group (four levels) as the main effect. The primary analysis will compare the 4.2 mg CA-008 group to the placebo group using a two-sided test at the  $\alpha=0.05$  level of significance.

### 15.6.2. Key Secondary Efficacy Analyses

If the primary efficacy analysis is statistically significant ( $p < 0.05$ ), then comparisons between the 4.2 mg CA-008 group and the placebo group will be made for the following endpoints:

- Percentage of subjects who do not require opioids or are opioid free (OF) from T0 to T96):  
OF0 to 96h
- Total opioid consumption (in daily oral morphine equivalents) = OC from T0 to T96h: OC0 to 96h
- Using NRS at rest: AUC0 to W1

Each of the above comparisons will be made using a two-sided test at the  $\alpha = 0.05$  level of significance. However, once a nonsignificant result occurs, then all subsequent analyses in the hierarchy will be exploratory rather than confirmatory.

The percentage of subjects who do not require opioids or are OF will be analyzed using a logistic regression model with treatment group (four levels) as a factor. The other two key secondary endpoints will be analyzed using the same type of ANCOVA model as described for the primary efficacy analysis.

### 15.6.3. Other Efficacy Analyses

For the primary endpoint and the three key secondary endpoints, comparisons between the 0.7 mg CA-008 group and the placebo group, and between the 2.1 mg CA-008 group and the placebo group will be tested using the same model as used for the primary (key secondary) analysis of the corresponding endpoint.

All other AUC and quantitative endpoints will be analyzed using the same type of ANOVA model as described for the primary analysis. All proportion endpoints will be analyzed using the same type of logistic regression model as described for the first key secondary efficacy analysis.

All other efficacy analyses will be conducted using two-sided tests at the  $\alpha = 0.05$  level of significance, with no adjustment for multiplicity.

### 15.6.4. Handling of Dropouts and Missing Data

All efforts will be made to minimize missing data. These efforts will include the following:

- Subjects are required to consent continuous data collection even after subjects discontinue the study treatment;
- Continue data collection after subjects taking rescue medication;
- Establish robust efficacy data collection procedures.

With the procedures above, it is expected that the missing would be minimal.

For subjects who take rescue medication a windowed last pain score carried forward (LOCF) will be used. The pre-rescue pain score will be used to impute scheduled assessments for 4 hours following the rescue use. Intermittent missing pain scores (due to subject sleeping, etc.) will not be imputed, and AUC will be calculated based on non-missing values. For subjects who drop out of the study prior to Day 15, scheduled assessments will first be imputed using the worst prior pain score carried forward (WOCF). As sensitivity analyses, the AUC will also be calculated where assessments after drop out will be imputed using LOCF, using the last scheduled non missing pain score prior to drop out.

For secondary continuous efficacy endpoints, similar methods as the primary analysis will be used. For categorical endpoints, when assessments are imputed for data after a subject discontinues from the study, a WOCF method will be used.

Sensitivity analysis of the primary efficacy variable using different methods of imputation for rescue medication may also be performed. Additional sensitivity analysis with different missing value imputation methods for subjects who drop out of the study may also be performed. All imputation methods for pain intensity will be documented in the SAP.

## **15.7. Analysis of Safety**

Safety analyses will be conducted using data from the Safety Population (as defined in [Section 15.3](#)).

Safety will be assessed through treatment-emergent AEs (TEAEs); hematologic, biochemical, and urinalysis laboratory parameters; vital signs measurements; ECGs; physical exam, surgical site and neurosensory assessments.

No formal statistical comparisons will be performed for safety endpoints.

### **15.7.1. Adverse Events**

Adverse events will be coded by system organ class (SOC) and preferred term using the Medical Dictionary for Regulatory Activities (MedDRA) reporting system. Treatment-emergent AEs are defined as any of the following:

- Non-serious AEs with onset on the date of treatment with the study treatment through Day 29 or Early Termination, whichever occurs first;
- Serious AEs with onset on the date of treatment with the study treatment through 30 days after Day 29 or Early Termination, whichever occurs first;
- AEs that start before the start of treatment but increase in severity or relationship at the time of or following the start of treatment through Day 29 or Early Termination, whichever occurs first.

The number and percentage of subjects with TEAEs will be displayed for each treatment group by SOC and preferred term. Additionally, TEAEs will be tabulated for each treatment group by severity and by relationship to the study treatment. A listing of SAEs will be provided if applicable.

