
Study Populations:
	
The following three analysis populations are planned for this study:
 
 
• The Safety Population will include all subjects who received any part of a dose of study treatment.
 
• The PK Population will include all subjects who receive a full dose of study treatment and complete all PK assessments through the T6h timepoint.
 

	
Subjects who fail to complete these PK assessments will be replaced.
 

• The intent-to-treat (ITT) population will include all subjects as randomized to study treatment. The modified intent-to-treat (mITT) Population will include all subjects who receive a full dose of study treatment and complete the first 3 pain assessments (through T2h).

• Inpatient study completers (Inpatient Completers) will include all subjects who receive a full dose of study treatment and complete the inpatient assessment period (through T96h).

• Study completers (Study Completers) will include all subjects who receive a full dose of study treatment and complete the entire study period through D29±2/W4.

 
Subjects who elect to discontinue study participation during the inpatient phase of the study, will be asked to continue with assessments through T96h if they have not elected to withdraw from all aspects of study participation. Subjects who elect to discontinue participation prior to D8 (W1) will be considered to have terminated as of the date of their election, however they will be asked to return to the site one time, if willing and at their convenience, to ensure wound healing.
 
All safety assessments and baseline characteristics will be summarized using the Safety Population. PK and efficacy analyses will be performed using the PK and mITT Populations, respectively. Additional efficacy analyses will be performed on the ITT, Inpatient Completer and Study Completer Populations. All summaries will be grouped by the actual treatment received. Each active dose cohort will be presented separately, along with a combined active dose group.

--	---

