#### **9.1.9. Early Termination Visit**

If willing, subjects who elect to prematurely discontinue from the study will be requested to come in at their convenience for the following assessments (if subjects are not willing to return for assessments, request that they at least come in to assess the surgical site to ensure adequate wound healing):

- Record vital signs (HR, BP and RR)
- Perform surgical site assessment and neurosensory exam of the foot proximal to the surgical site with contralateral comparison
- Document concomitant medication use including doses and times taken for analgesic medications
- Document concomitant treatment use
- Record AE Assessment

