### 15.3. Analysis Populations

The following three analysis populations are planned for this study:

- The Safety Population will include all subjects who received at least part of a dose of study treatment.
- The PK Population will include all subjects who receive a full dose of study treatment and complete at least all PK assessments through the T6h timepoint. Subjects who fail to complete these PK assessments will be replaced.
- The modified ITT (mITT) Population will include all subjects who receive a full dose of study treatment and complete the first 3 pain assessments (through T2h).

Subjects who elect to discontinue study participation during the inpatient phase of the study, will be asked to continue with assessments through T96h if they have not elected to withdraw from all aspects of study participation. Subjects who elect to discontinue participation after discharge from the inpatient unit but prior to D8 (W1) will be considered to have terminated as of the date of their election, however they will be asked to return to the site to reassess the surgical site for wound healing.

All safety assessments and baseline characteristics will be summarized using the Safety Population. PK and efficacy analyses will be performed using the PK and mITT Populations, respectively. All summaries will be grouped by the actual treatment received. Each active dose cohort will be presented separately, along with a combined active dose group.

Inpatient Study Completer will be defined as those subjects who complete the assessments through T96h. Outpatient Study Completer will be defined as those subjects who complete the assessments through D29±2 (W4).

Membership in the analysis populations will be determined before unblinding.

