- Duration of an AE will be computed in days for AEs lasting longer than 24 hours, and as hours for AEs lasting less than 24 hours. Duration in hours will be calculated as the stop date/time of the event minus the start date/time. Duration in days will be calculated by using stop date minus the start date + 1 if AE occurs on or after taking study medication. If AE occurs prior to the study medication, then the duration will be calculated by using stop date minus the start date; If reported as ongoing at the time of database lock, the duration will be calculated using the date of the last visit or the last date of any AE for the subject in the database, whichever is later. Missing dates will be imputed as described in Table 8-1.
- The date/time of early termination will be the date/time that the subject confirms they no longer want to participate in the study, regardless of whether they decide to withdraw from all or only some study procedures and regardless of if they return for to the site for assessment of wound healing.
- The number of days in the study is computed as: [Date of study completion or withdrawal minus the date of study drug administration] + 1.
- If duplicate values are obtained at a given visit (e.g., repeated vital sign measurements), the last value will be used unless it is noted that the measurement was in error for that value. Values that compromise interpretation will not be used in summaries (e.g., values that were obtained post-dose will not be summarized as pre-dose values).

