8.2 Adverse Events

Any untoward medical event that occurs after signing the informed consent form (ICF) is considered to be an adverse event (AE). All AEs will be recorded through 29 days (or 36 days as applicable) or ET, after the completion of surgery. SAEs will be recorded until 30 days after the 29 day follow up visit or ET, whichever occurs earlier. Treatment-emergent AEs are defined as AEs that start or worsen in severity after the end of study treatment infiltration (post T0). Verbatim terms used by investigators to identify AEs in the CRFs will be mapped to the appropriate preferred term (PT) and system organ class (SOC) using a standardized coding dictionary (MedDRA Version 21.0). All coding will be reviewed prior to database lock. All recorded AEs will be listed, but only TEAEs will be summarized.

For evaluation of causal relatedness to treatment, the categories are probably related, possibly related or unlikely related. For categorization in the summary tables, AEs designated as probably or possibly related will be considered to be related.

For the evaluation of event severity terms, the criteria are mild, moderate, severe or potentially life-threatening.

In addition to a listing of all TEAEs, treatment related TEAEs, serious TEAEs, Deaths, and TEAEs leading to premature discontinuation from the study will be provided.

An overall summary will be prepared giving for each treatment group and overall both the number of TEAEs, and the number of subjects with at least one TEAEs, as well as SAEs, treatment related TEAEs and TEAEs leading to premature discontinuation from study.

The number of subjects with AEs will be summarized for each treatment group by SOC and PT sorted in alphabetically by SOC, and then by PT within SOC. These summaries will be given by treatment in separate tables for each of the following TEAE event sets:

- All events
- Treatment related events
- Serious events
- Events leading to premature discontinuation from study
- Events by maximum severity

If a given subject experiences a TEAE that maps to the same PT/SOC more than once, the subject will be counted only once for the SOC/PT at the greatest severity (i.e., mild, moderate, or severe) and causality (i.e., attribution to study material).

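### The protocol and SAP disagree on when the non-serious TEAE window closes, and AEs starting after a subject's decision to stop can be left out although the plan still looks for them

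*Protocol*

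**What the plan says.** **End of the window, Protocol 15.7.1.** The first bullet covers "Non-serious AEs with onset on the date of treatment with the study treatment through Day 29 or Early Termination, whichever occurs first". The third bullet closes the window at the same point for AEs that began before treatment and then worsened. The second bullet gives serious AEs longer: "Serious AEs with onset on the date of treatment with the study treatment through 30 days after Day 29 or Early Termination".

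**TEAE definitions without that end.** SAP 8.2 counts AEs that start or worsen after T0. The Protocol synopsis (safety assessment times and safety endpoints) counts AEs after T0, and Protocol 9.1.4 counts all AEs from study treatment onward. None of these definitions stops at ET. Protocol 12.5.9 and 13.1.2 also document non-serious AEs to Day 29 or, if needed, Day 36, without mentioning ET.

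**Recording period, SAP 8.2.** "All AEs will be recorded through 29 days (or 36 days as applicable) or ET, after the completion of surgery". The same section lists every recorded AE but summarizes only TEAEs.

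**Date of ET, SAP 3.** "The date/time of early termination will be the date/time that the subject confirms they no longer want to participate in the study". This applies whether the subject refuses all procedures or only some, and "regardless of if they return for to the site for assessment of wound healing". The synopsis dates it the same way for one group: "Subjects who elect to discontinue participation prior to D8 (W1) will be considered to have terminated as of the date of their election". Protocol 15.3 has similar wording, limited to those who stop after discharge and before D8.

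**Observation after that date.** Protocol 15.3 and SAP 2.2 ask inpatients who stop to continue assessments to T96h, unless they withdraw from everything. Of those who stop after discharge but before D8, Protocol 15.3 says "however they will be asked to return to the site to reassess the surgical site for wound healing". The ET visit in Protocol 9.1.9 includes a surgical-site assessment, a neurosensory exam and an AE assessment. For subjects unwilling to return for all of these, sites are to "request that they at least come in to assess the surgical site to ensure adequate wound healing".

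**The concern.** Treatment is a single intraoperative dose, so a decision to leave the study does not end exposure. A window that closes at that decision leaves out a period in which the drug may still be acting and in which the plan deliberately keeps looking for AEs.

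Local tolerability is a main safety question for an agent placed in the wound. Protocol 15.7.4 has abnormal surgical-site findings recorded as AEs, and Protocol 12.5.8 does the same for persistent atypical sensory change. Many such events would be non-serious. Protocol 15.7 plans no formal safety comparisons, so the tabulated TEAE incidences are the result that readers will use. If the documents allow two cut-offs, two programmers can produce different tables from the same data.

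**Working it through.** The plan states no figure on this point, so the check is a comparison of rules followed by simple arithmetic on the gap.

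**Step 1. The event in question.** Take a non-serious AE with onset after the subject's decision to stop and before the last planned safety observation. That observation is the end of continued inpatient assessment at T96h, or the ET or wound-check visit.

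**Step 2. Is it counted?** The answer depends on which rule is used and on what ET means.

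| Rule applied | ET = decision (SAP 3) | ET = visit |
|---|---|---|
| Protocol 15.7.1 window | Outside, not a TEAE | Inside, if onset is by the visit |
| SAP 8.2 definition and recording period | A TEAE by definition, but after recording has stopped | Recorded and a TEAE |

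Under the only dating rule that the SAP gives, the event drops out by either route. Under the visit reading it is kept. Protocol 15.7.1 does not say which meaning applies, and SAP 12 lists no departure from it.

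**Step 3. What is not affected.**
- 15.7.1 turns on onset. An AE first seen at the wound check that began on or before the decision is still treatment-emergent. If the rule is applied by calendar date, onsets on the day of the decision count too.
- Serious AEs have 30 further days.
- Surgical-site and neurosensory results are summarized by treatment and visit whatever their TEAE status (SAP 8.3 and 8.6; Tables 14.3.5, 14.3.6.1 and 14.3.6.2).

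**Step 4. Length of the gap for an inpatient.** For a decision at hour t and a stay to T96h, the gap is 96 − t hours:
- t = 12: 84 h
- t = 24: 72 h, which is 72/96 = 75% of the inpatient period
- t = 48: 48 h
- t = 72: 24 h

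For an outpatient, the gap runs from the decision to the return visit. The documents do not fix its length.

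**Step 5. Effect on incidence.** The planned size is 36 per arm (Protocol 15.2). One subject whose only qualifying AE is lost changes the arm's incidence by 1/36 = 2.8 percentage points. The change is zero if that subject already has a counted AE in the same category.

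The documents give no drop-out rate. As an assumption, take 1 to 4 early terminators per arm. The ceiling, reached only if every one of them has a first AE in the gap, is then 1/36 to 4/36, or 2.8 to 11.1 points.

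The relative effect depends on the base. These are hypothetical counts, with one subject lost:
- An uncommon event: 3/36 (8.3%) becomes 2/36 (5.6%).
- Any TEAE: 18/36 (50.0%) becomes 17/36 (47.2%). For scale, the Phase 1 study in the Protocol's Table 2 reports TEAEs in 55.2% of active and 50.0% of placebo subjects.

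**The case against.** The strongest reply is that the SAP governs the tables. Protocol 15.1 leaves the final analysis to it, and its TEAE definition is open-ended, so any AE that is recorded after the decision would be counted. Moreover, ET is often a visit in these documents. The synopsis requires an ET visit, Protocol 9.1.9 describes one, and Protocol 12.5.7 and 12.5.8 pair Day 29 with ET as visits. Protocol 15.7.1 also sets ET beside Day 29, so the visit is a natural reading there. The decision-date rule for all discontinuers is a SAP convention, joined here to a protocol definition that the SAP does not repeat.

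Much of this stands. It shows that the loss is not certain. It does not remove the problem, because an open definition cannot count events that were never recorded, and SAP 8.2 ends recording at ET. The visit reading also leaves no end date for a subject who declines the visit.

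A reader might infer that every AE found at the later wound check is excluded. The documents do not support that, because the rule depends on onset. A problem that led the subject to stop began before the decision and is inside the window. Nor do the documents show that local safety data are lost altogether, since wound and neurosensory findings have their own summaries and all recorded AEs are listed.

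**Conclusion.** The concern holds as a conflict over the end of the non-serious TEAE window. Followed as written, with ET dated by SAP 3, the plan leaves out non-serious AEs, and worsening of pre-treatment AEs, with onset between the decision to stop and the last planned safety observation.

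The effect is up to 2.8 percentage points of an arm's incidence per subject lost, assuming 36 per arm and no other counted AE of that kind in the subject. The total cannot be computed without a drop-out rate. A reader might also infer a bias between arms, for instance if more placebo subjects stop for lack of efficacy. That is possible, but nothing in the documents shows that stopping will differ by arm.

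This affects descriptive safety tables and leaves the efficacy analysis untouched. It is worth correcting because the ambiguity is avoidable and the correction is cheap.

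**What to change.** Use one TEAE definition in Protocol 15.7.1 (first and third bullets) and SAP 8.2, along these lines: *Non-serious AEs that start or worsen after T0 are recorded and counted through the subject's last safety assessment actually made, including inpatient assessments continued to T96h and the ET or wound-check visit, up to the Day 29 visit, or the Day 36 visit if held.*

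In SAP 8.2, change the recording sentence for AEs only and leave the serious AE window as it is. Add to SAP 3 that the decision date is used for disposition and ends neither AE recording nor the TEAE window. The limit must allow for Day 36. A cut-off at the earlier of Day 29 and the last assessment would drop AEs up to a Day 36 visit that both documents provide for.

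The cost is a few sentences and no new visits, since the assessments are already planned. TEAE incidence may be slightly higher, and follow-up will vary in length among early terminators.
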